8.6.5. Pharmacodynamic Assessment

Approximate quantitation of infused study drug bound to PD-1 receptors on the surface of T cells in the peripheral blood and within the resected tumor and lymph node specimens will be performed in [name] laboratory, according to published procedures⁸⁷. This will provide information about tissue penetration of the study drug(s), which has not been obtainable in prior studies.

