1.2. Durvalumab

The non-clinical and clinical experience is fully described in the current version of the durvalumab (MEDI4736) Investigator's Brochure.

Durvalumab is a human monoclonal antibody (mAb) of the immunoglobulin G (IgG) 1 kappa subclass that blocks the interaction of PD-L1 (but not programmed cell death ligand-2) with PD-1 on T cells and CD80 (B7.1) on immune cells (IC). It is being developed by AstraZeneca/MedImmune for use in the treatment of cancer (MedImmune is a wholly owned subsidiary of AstraZeneca; AstraZeneca/MedImmune will be referred to as AstraZeneca throughout this document.) Durvalumab has been engineered to reduce antibody-dependent cellular cytotoxicity and complement-dependent cytotoxicity. In vitro studies demonstrate that durvalumab antagonizes the inhibitory effect of PD-L1 on primary human T cells, resulting in their restored proliferation and release of interferon gamma (IFNy; Stewart et al. 2015).

To date durvalumab has been given to more than 1800 patients as part of ongoing studies either as monotherapy or in combination with other anti-cancer agents. Details on the safety profile of durvalumab monotherapy are summarized in Section 1.13.1. Refer to the current durvalumab Investigator's Brochure for a complete summary of non-clinical and clinical information including safety, efficacy and pharmacokinetics.

18 Nov 2020 Page **40** of **164**

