1.3. Tremelimumab

The non-clinical and clinical experience is fully described in the current version of the tremelimumab Investigator's Brochure.

Tremelimumab is a human immunoglobulin (Ig) G2 mAb that is directed against CTLA-4; cluster of differentiation [CD]152), a cell surface receptor that is expressed primarily on activated T cells and acts to inhibit their activation. Tremelimumab completely blocks the interaction of human CTLA-4 with CD80 and CD86, resulting in increased release of cytokines (interleukin [IL]-2 and interferon [IFN]-γ) from human T cells, peripheral blood mononuclear cells and whole blood (Tarhini and Kirkwood 2008). Tremelimumab is being developed by AstraZeneca for use in the treatment of cancer.

To date tremelimumab has been given to more than 1000 patients as part of ongoing studies either as monotherapy or in combination with other anticancer agents. Details on the safety profile of tremelimumab monotherapy are summarized in Section 1.13.1. Refer to the current tremelimumab Investigator's Brochure for a complete summary of non-clinical and clinical information including safety, efficacy and pharmacokinetics.

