1.7. Rationale for Neoadjuvant Immunotherapy plus Radiation Therapy in Stage III NSCLC

1.7.1. Anti-PD-1/PD-L1 is Safe and Effective in NSCLC

With ~20% response rates (RR) in pre-treated NSCLC and durable responses in a subset of patients, anti-PD-1/PD-L1 agents including durvalumb (anti-PD-L1) are efficacious in NSCLC⁵⁴⁻⁵⁸. Combined anti-PD-L1 plus CTLA-4 inhibition with durvalumab plus tremelimumab has also resulted in remarkable RRs of up to 23% in pre-treated NSCLC⁵⁹, and is being studied in front-line NSCLC trials (NCT02453282, NCT02542293).

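### Section 8.6.5 measures study drug bound to PD-1, but the protocol gives PD-L1 and CTLA-4 as the drugs' targets, so the assay as written cannot support its tissue-penetration statement

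*Combined protocol and SAP*

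**What the plan says.** Section 8.6.5 (Pharmacodynamic Assessment) plans "Approximate quantitation of infused study drug bound to PD-1 receptors on the surface of T cells" in blood and in the resected tumour and lymph nodes, following a published procedure (reference 87). It then states the purpose: "This will provide information about tissue penetration of the study drug(s), which has not been obtainable in prior studies".

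The protocol describes its two drugs differently. Section 1.2 says that durvalumab "blocks the interaction of PD-L1 (but not programmed cell death ligand-2) with PD-1 on T cells", and Section 1.7.1 labels it outright: "anti-PD-1/PD-L1 agents including durvalumb (anti-PD-L1) are efficacious in NSCLC". Section 1.3 says "Tremelimumab is a human immunoglobulin (Ig) G2 mAb that is directed against CTLA-4". Table 11 in Section 16.1 lists these two and no other investigational product.

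**The concern.** A receptor-occupancy measurement is informative only if the drug binds the receptor being measured. Section 8.6.5 names PD-1, which is the partner of durvalumab's target rather than the target itself, and is unrelated to tremelimumab's target.

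At stake is the only listed correlative method that is meant to show whether drug reaches tumour and nodes. If the section is followed literally, limited surgical tissue could go to a measurement that cannot answer that question, and the result would have no clear interpretation.

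**Working it through.** No arithmetic applies. The check is whether the assay's stated target matches the drugs' stated targets, and whether anything else in the protocol corrects or replaces the assay.

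1. **What the assay measures.** Section 8.6.5 specifies drug bound to PD-1 on the T-cell surface, in blood, tumour and nodes.

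2. **What the drugs bind.**

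| Agent | Cohort | Target in the protocol | Where stated | Matches PD-1? |
|---|---|---|---|---|
| Durvalumab | 1 and 2 | PD-L1 | 1.2, 1.7.1, 1.8 | No |
| Tremelimumab | 2 only | CTLA-4 | 1.3 | No |

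The Section 1.2 sentence, read alone, says which interaction is blocked and not which partner is bound. The class label in Section 1.7.1 settles that the bound partner is PD-L1.

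3. **Whether another drug could be bound to PD-1.** Prior PD-1 agents are excluded (Section 4.2, criterion 4), and PD-1 antibodies are prohibited during study treatment (Table 5). No permitted on-study drug is an anti-PD-1 antibody.

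4. **Whether this is loose wording for the PD-1 pathway.** The sentence names a receptor and a cell surface. The title of reference 87 is that of a phase I study of single-agent anti-PD-1 treatment. The named target and the cited method therefore agree with each other and disagree with the study drugs. Section 8.6.1, in the same group of methods, describes the regimen correctly as anti-PD-L1 with or without anti-CTLA-4, so 8.6.5 is the outlier.

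5. **Whether another listed method fills the gap.** Sections 8.6.1 to 8.6.9 and the exploratory plan in 12.4 specify no assay of drug bound to PD-L1 or CTLA-4, no drug-concentration assay and no soluble PD-L1 assay. Soluble PD-L1 appears in the dose rationale (Section 1.9). Section 8.6.9 leaves serum testing open-ended but does not name it.

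6. **What depends on the result.** Drug binding and tissue penetration are not named in the exploratory objectives (synopsis and Section 2.3) or in Sections 12.4.1 and 12.4.2, where the analyses are described as descriptive. No safety or feasibility rule uses the assay.

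**The case against.** The strongest reply is that the mismatch is clear but the assay's result is not predictable. Section 8.6.5 gives no detection reagent or readout and defers to a publication of which the documents show only the title. If that procedure detects infused antibody on the T-cell surface, rather than the PD-1 receptor, it might register drug bound elsewhere: Sections 8.6.3 and 8.6.4 list PD-L1 among the T-cell markers, and Section 1.3 says CTLA-4 is expressed mainly on activated T cells.

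This stands, and it limits the point. A reader might infer that every patient would show no binding or only background. The documents do not support that, because they do not say what is detected. It does not rescue the section, however. A signal of that kind would not be the PD-1-bound drug that the section says it quantifies, and nothing in the text would allow it to be read as drug at PD-L1 or CTLA-4.

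A second tempting inference is that specimens from all 32 planned evaluable patients (16 + 16) would be wasted. The documents assign no specimens to this assay. Section 8.5.1 collects blood for general PBMC, plasma and serum isolation, Table 9 has only generic biomarker rows, operative tissue serves several analyses (Sections 8.3 and 8.4.1.3), and tissue exists only for patients who are resected. No extra draw or biopsy is shown to depend on it.

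It is also fair to say that an exploratory result which feeds no decision has little capacity to mislead. That supports a low priority. It does not support leaving the wrong target in place.

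**Conclusion.** The point holds as a mismatch between method and drugs. Section 8.6.5 specifies an assay for drug bound to PD-1 and cites an anti-PD-1 antibody study, while the protocol's own descriptions place durvalumab at PD-L1 and tremelimumab at CTLA-4. As written, the assay measures drug at neither target and cannot support the tissue-penetration statement in either cohort. No other section corrects it.

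The size is small: one exploratory readout, with no effect on the primary safety and feasibility endpoints, the secondary endpoints, the Bayesian stopping rules or the sample size. The conclusion rests on the protocol's drug descriptions and on the title of reference 87. It does not assume any particular assay result. The text may have been carried over from an anti-PD-1 study, but the documents do not say so and the point does not need it.

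**What to change.** In Section 8.6.5, replace PD-1 with PD-L1 (both cohorts) and add CTLA-4 (cohort 2). Replace reference 87 with a method and reference suited to those targets and to the material already planned: PBMCs (Sections 8.5.1 and 8.5.2) and the cryopreserved single-cell suspensions from surgery (Section 8.4.1.3). State the readout and the cell population. A T-cell-only measurement may be too narrow for durvalumab, since Section 1.1.1 places PD-L1 on tumour cells as well as on infiltrating immune cells.

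If no suitable assay is available, delete the section together with its tissue-penetration sentence. The documents do not show whether such assays exist or work on cryopreserved cells, so the laboratory should confirm this before the text is changed.

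Soluble PD-L1 in the serum or plasma already collected could be added as a systemic marker of durvalumab target engagement. It says nothing about penetration into tumour or nodes and does not measure tremelimumab, so it cannot stand in for the tissue assay.

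The cost is a short text amendment plus some assay set-up, or the loss of one exploratory readout if the section is deleted.

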8.6.6. Genomic and Mutation-associated neoantigen (MANA) Analyses

Genomic analyses will be performed by whole-exome sequencing in pre and post-treatment tumor tissue and matched normal tissue, to assess dynamics in the mutational landscape using described methods^{88, 89}. A multi-dimensional neoantigen prediction algorithm that incorporates MHC binding affinity, epitope processing, self-similarity and gene expression to generate neoantigen candidates tailored to each individual's HLA haplotype will be used as previously described⁸⁹. The TCR repertoire will be assessed serially by means of TCR sequencing as previously described⁸⁹.

8.6.7. Immune Functional Assays

To assess functional recognition of MANAs, we will complete immune functional assays on PBMC and TIL where applicable, using a new assay called MANAFEST (MANA Functional Expansion of Specific T-cells), developed at the Bloomberg-Kimmel Institute. This assay assesses expansion of T-cell clones based on deep sequencing of TCRbeta CDR3 regions. MANAFEST antigens will be validated by multiplex tetramer staining.

8.6.8. Liquid Biopsy Analysis

ctDNA dynamics will be assessed by targeted sequencing of serial plasma samples collected at the time intervals specified in the study timeline. For these analyses, we will use a custom capture and

18 November 2020 Page **92** of **164**

sequencing approach called targeted error correction sequencing (TEC-Seq) that allows for sensitive and specific detection of low abundance sequence alterations using next generation sequencing⁹⁰.

8.6.9. Serum Analysis

Serum will be assessed for immunological factors which may include antibodies, cytokines and chemokines, as well as potentially for circulating tumor DNA.

8.6.10. Leftover Samples

Any leftover study blood and tissue samples will be stored in the Immunology Laboratories at Johns Hopkins for future research studies. These samples may be released for use in future studies after approval by the principal investigator and other regulatory bodies, as appropriate. Subjects will be asked to consent to the future use of samples in the consent document.

8.6.11. Additional Information

The study coordinator will keep a log (separate logs will be kept for the blood and tissue samples) that includes the study number, a specimen serial number, the patient's name, time point in therapy, and the date and time that the sample was drawn. The sample will be labeled with a serial number only. The laboratory technician will keep a log with the specimen number, conditions, processing and storage information. The laboratory investigators will be blinded to the subject identifiers and clinical data while generating the research data; additionally, the reported results will not disclose any unique patient identifiers.

Note: The correlative sample collection schedules outlined above are based on an ideal subject. The sample schedule should be followed as closely as is realistically possible; however, the schedule may be modified due to problems such as scheduling delays or conflicts (e.g., clinic closure, poor weather conditions, vacations, etc.)

8.6.12. PD-L1 Testing

To ensure comparability of data across all studies of durvalumab and/or tremelimumab and to gain real world experience on the performance of this assay, it is strongly encouraged that all studies that include PD-L1 testing utilize the Ventana SP263 assay. Testing should be restricted to the Ventana SP263 assay and should be performed in accordance with the package insert on the Ventana Benchmark platform (Ultra or XT).

The Ventana SP263 assay is fully analytically validated test characterized through to the completion of reader precision studies in the non-small cell lung cancer (NSCLC) and squamous cell carcinoma of the head & neck (SCCHN). For these tumors, the Ventana SP263 assay has a fully reproducibility data package supporting cut-off and scoring algorithm. Following completion of ATLANTIC and HAWK clinical trials, the assay will be associated with clinical utility. In other cancer types (bladder, pancreatic, gastric, hepatocellular, triple negative breast, ovarian, esophageal, nasopharyngeal,

18 November 2020 Page **93** of **164**

glioblastoma, soft tissue sarcoma, cholangiocarcinoma, small cell lung, melanoma and cervical HPV + cancers), the Ventana SP263 assay has only limited clinical performance data.

Sample collection for PD-L1 testing

- The preferred tumor sample for the determination of a patient's PD-L1 status is the one taken following the completion of the most recent prior line of therapy. Samples taken at this time reflect the current PD-L1 status of the tumor and considered clinically most relevant.
- In AstraZeneca studies, the preferred sample for PD-L1 testing was less than or equal to 3
 months old. In cases where a sample a less than 3 months old was not available, patients
 were asked to undergo a new biopsy if considered clinically appropriate by their treating
 physician.
- Samples should be collected via a core needle of 18 gauge or larger or be collected by an
 incisional or excisional tumor biopsy. Where institutional practice uses a smaller gauge
 needle, samples should be evaluated for tumor cell quantity (ie. >100 tumor cells) to allow
 for adequate PD-L1 immunohistochemistry analyses.
- When the collection of a new sample is not clinically appropriate, archival samples may be
 utilized provided the specimen it is not older than 3 years of age. When archival samples are
 used to assess PD-L1 status, the age of the sample/date of collection should be captured.
- Samples submitted for PD-L1 testing should be formalin fixed and embedded in paraffin.
 Samples from fine needle aspirates (FNA) or decalcified bone are not appropriate for PD-L1 analysis.

Sample data collection for PD-L1 testing

The following fields of data should be collected from the site/institution collecting and if, indicated shipping of the samples:

- Patient identifier (ecode or unique identifier)
- Specimen identifier (written on the specimen)
- Site identifier
- Specimen collection date
- Type of specimen submitted
- Quantity of specimen
- Date of sectioning
- Archival or new biopsy/tissue
- Tumor type

18 November 2020 Page **94** of **164**

- Primary tumor location
- Metastatic tumor location (if applicable)
- Fixative

The following fields of data should be collected from PD-L1 testing laboratory:

- Are the negative and positive controls stained correctly
- Is the H&E material acceptable
- Is morphology acceptable
- Total percent positivity of PD-L1 in tumor cells
- PD-L1 status (positive, negative or NA) in tumor cells
- Total percent positivity of PD-L1 in infiltrating immune cells

The Ventana SP263 assay to measure PD-L1 in tumors is experimental. As with all tests, there is a chance of false positive (the test shows high PD-L1 when it is not there) or false negative (the test does not show PD-L1 when it is there) results may occur.

Sample processing and if indicated submission process for PD-L1 testing

Preparing Stored samples for testing

Where samples already exist, they should be retrieved from the Bio-Bank storage location. These blocks should undergo quality review, prior to evaluation or shipment. Where it is not possible or indicated to ship the block to a testing laboratory, unstained slides should be prepared from the paraffin-embedded tumor sample block (described below) prior to evaluation or shipment.

Preparing newly acquired samples for PD-L1 testing

If patients are undergoing a biopsy procedure that provides the option to submit newly acquired samples, this sample should be used to determine PD-L1 status, from one core biopsy that is inidividually processed into am FFPE block.

It is recommended that core needle tumor biopsies are collected using an 18 gauge or larger needle and the process should be image-guided. Excisional or incisional samples are also adequate. If this is not per the institutions normal practice and a smaller gauge needle is used then the number of cores collected should be increased to allow sufficient material for successful PD-L1 testing (>100 tumor cells) and embedded in the same block. If available, a single excisional biopsy of at least 4 mm in diameter may substitute for all core biopsies.

Fixation of biopsy samples for PD-L1 testing

Previously frozen tissue is not acceptable for processing to FFPE for PD-L1 testing. To fix newly acquired tissue, place immediately (within 30 min of excision) into an adequate volume of 10% v/v

18 November 2020 Page **95** of **164**

neutral buffered formalin (NBF). Core biopsies and resection specimens should remain in fixative for 24 and 48 hours respectively at room temperature.

It is vital that there is an adequate volume of fixative relevant to the tissue (at least a 10 volume excess) and that large specimens (if any) are incised prior to fixation to promote efficient tissue preservation.

Embedding in paraffin for PD-L1 testing

An overnight processing schedule into paraffin wax is recommended

Storage of tumor blocks for PD-L1 testing

FFPE blocks and 20 ml whole blood for serum isolation should be stored at -20 degrees Celsius and protected from light until shipment by courier at, as detailed at timepoints In the study schema when tissue is obtained.

Quality control of samples to be used for PD-L1 testing

Tissue should be assessed by the site pathologist prior to PD-L1 testing.

Each sample should be reviewed for:

- Adequate fixation
- Good preservation of morphology
- Presence of tumor tissue
- Histopathology consistent with indication
- Greater than 100 tumor cells are required to determine PD-L1 status tumor cell content must be reviewed prior to testing in order for PD-L1 obtain a valid result.

If indicated, shipping samples to a PD-L1 testing laboratory

When submitting sample to for PD-L1 testing the recommendation is to ship the block in order for sectioning to occur at the laboratory. Blocks should be shipped - containing enough material to be provided to allow a minimum of 5, and preferably 10, sections to be cut (each 4 microns thick) to be used for PD-L1 testing.

Sectioning instructions

- Where it is not possible or indicated to ship the block to laboratory for PD-L1 testing, unstained slides should be prepared from the paraffin-embedded tumor sample block as described below:
- A minimum of 4 x 5 micron (μm) thick, unstained sections should be provided for PD-L1 testing
- A new disposable microtome blade must be used for each block to prevent contamination between patient samples

18 November 2020 Page **96** of **164**

- Apply one section per slide to positively-charged Superfrost glass slides
- The sections should be dried overnight between room temperature and 37°C. Do not dry sections at temperatures above 37°C.

Sections should be stored at -20 degrees Celsius and protected from light until use or shipment to testing lab by courier at ambient temperature. It is recommended that slides are cut freshly prior to PD-L1 testing and they are used within 90 days of being cut to obtain PD-L1 status.

8.6.13. Estimate of volume of blood to be collected

The total volume of blood that will be drawn from each subject in this study is as follows:

TABLE 9. VOLUME OF BLOOD TO BE DRAWN FROM EACH SUBJECT

Assessment		Sample volume (mL)	No. of samples	Total volume (mL)
Safety	Clinical chemistry	5ml	7	35ml
	Hematology	5ml	7	35ml
Biomarker		120ml	3	360ml
Biomarker		80ml	3	240ml
Total				670mLs

8.7. Withdrawal of informed Consent for Donated Biological Samples

As collection of required biological samples is an integral part of the study, then the subject is withdrawn from further study participation. If a subject withdraws consent for the use of leftover samples, the samples will be disposed of/destroyed, and the action documented. The Principal Investigator will ensure:

- Biological samples from that subject, if stored at the study site, are immediately identified, disposed of /destroyed, and the action documented
- The laboratory(ies) holding the samples is/are informed about the withdrawn consent immediately and that samples are disposed/destroyed, the action documented and the signed document returned to the study site
- The subject is informed about the sample disposal.

18 November 2020 Page **97** of **164**

9. Assessment of Safety

The Principal Investigator is responsible for ensuring that all staff involved in the study is familiar with the content of this section.

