3.1.2. Determination of Eligibility

After eligibility is established, the study staff will register participants. The following are required to be submitted for successful registration:

Registration forms 🔛

Copy of subject consent 🔛

Copies of the following documents:

- Diagnostic pathology report(s) [SEP]
- PET/CT or CT scan report, MRI or CT brain with contrast report
- Laboratory reports including: [stp]

o Complete blood count (CBC) with differential (including absolute lymphocyte count) and direct platelet count.

18 Nov 2020 Page **55** of **164**

- o Chemistry: Albumin, SGOT (AST), SGPT (ALT), Bilirubin (direct and total), Calcium, Creatinine, Glucose, Total protein, Urea nitrogen, Uric Acid, Electrolytes (including sodium, potassium, chloride and bicarbonate).
- o Liver function tests (AST, ALT, Total bilirubin, alkaline phosphatase)
- o Urinalysis (routine)
- o Baseline thyroid immune safety assay: Thyroid Stimulating Hormone (TSH). Abnormal endocrine results should be followed up per standard of care, and may require an endocrine consult and additional testing.
- o Pulmonary function report
- o Other documents, if requested.

Study treatment cannot begin until the patient is registered. Subjects who sign a consent form, but do not initiate protocol treatment for any reason (e.g., subjects who are screen failures), will be replaced and will not count towards our accrual goal. Also patients who do not stay enrolled through the DLT period, will be replaced and not count towards our accrual goal.

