4.5. Withdrawal of Consent

Subjects are free to withdraw from the study at any time (IP and assessments) without prejudice to further treatment.

Subjects who withdraw consent for further participation in the study will not receive any further IP or further study observation, with the exception of follow-up for survival, which will continue until the end of the study unless the patient has expressly withdrawn their consent to survival follow-up. Note that the patient may be offered additional tests or tapering of treatment to withdraw safely.

A subject who withdraws consent will always be asked about the reason(s) for withdrawal and the presence of any AE. The Investigator will follow up AEs outside of the clinical study.

If a patient withdraws consent, they will be specifically asked if they are withdrawing consent to:

- all further participation in the study including any further follow up (eg, survival contact telephone calls)
- withdrawal of consent to the use of their study generated data
- withdrawal to the use of any samples

18 Nov 2020 Page **65** of **164**

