12.4.2. Analysis of Exploratory Endpoints

These exploratory analyses will be descriptive/graphical in nature, and are designed to generate new hypotheses to be tested in future clinical studies. When parameters of immune response are measured, continuous variables will be summarized with means and standard deviations. Dichotomous and categorical variables will be summarized using proportions with exact 95% confidence intervals and counts, respectively. These summaries will be computed for each treated patient at multiple time points before and after immunotherapy administration as indicated in the study schema. Plots will be used to show the changes in immune response over time both for each individual. For each patient, comparisons in the pre and post-durvalumab (cohort 1) or durvalumab+tremelimumab (cohort 2) responses will be compared using paired t-tests (or Wilcoxon signed rank tests if appropriate) for continuous variables and McNemar's test for dichotomous or categorical variables. Associations between immune responses will be explored graphically (e.g. scatterplots, boxplots) and numerically (e.g. correlations, $\chi 2$ tests). Similar comparisons will be performed between immunoradiation-treated patients, and control patients with stage III resectable NSCLC who do not receive immunoradiation, but are enrolled on a companion tissue collection protocol

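### Section 8.7 takes a patient off study for withdrawing consent to required samples, so later primary-endpoint observations may go uncollected, and Section 4.5 does not say what should follow

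*Combined protocol and SAP*

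**What the plan says.** - Section 8.7, first sentence: "As collection of required biological samples is an integral part of the study, then the subject is withdrawn from further study participation". No if-clause is printed, so the trigger has to be read from the section heading.
- Section 8.7, leftover samples: "If a subject withdraws consent for the use of leftover samples, the samples will be disposed of/destroyed, and the action documented". No removal of the patient is attached to this.
- Section 4.5: on withdrawal of consent, patients are asked item by item: "they will be specifically asked if they are withdrawing consent to" all further participation, use of study data, or, as its own item, "withdrawal to the use of any samples". The consequence of choosing the samples item alone is not stated.
- Section 4.5, effect of withdrawing from participation: the patient "will not receive any further IP or further study observation". Survival follow-up is the exception and continues by default. Adverse events are then followed outside the study.
- Section 12.1: an evaluable patient has had at least one dose and has complete toxicity follow-up. Each cohort accrues 20 to obtain 16 evaluable.
- Section 3.1.2: "patients who do not stay enrolled through the DLT period, will be replaced and not count towards our accrual goal". Section 4.6 also replaces patients who withdraw, and Section 6.3 replaces those who leave the DLT period for reasons other than DLT. Section 4.2, item 27, says that withdrawn patients are not replaced.
- Section 12.4.2, on the marker analyses: "These exploratory analyses will be descriptive/graphical in nature, and are designed to generate new hypotheses to be tested in future clinical studies".

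**The concern.** Safety and feasibility are the primary endpoints, and the marker work is exploratory. A rule that ends observation of the primary endpoints because a patient no longer consents to required samples gives up the more important data for the less important, even when the patient would accept all other follow-up. Asking about samples as a separate item, as 4.5 does, has little purpose if refusing them ends participation.

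The rule is also out of step with the rest of the protocol. Patients who do not complete radiation (6.2.2.5), who become suitable only for pneumonectomy (6.2.3.1) or who miss planned doses (6.2.3.3) are replaced but stay in safety follow-up. Section 8.7 has no such provision.

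At stake are the DLT and adverse-event observations, the time to surgery and the recurrence follow-up that would have been recorded after the withdrawal, in cohorts of 16.

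**Working it through.** **1. What the passages imply in sequence.** Take a treated patient who withdraws consent for required samples only.
- 8.7: withdrawn from further participation.
- 4.5: no further study observation except survival, with adverse events followed outside the study.
- 12.1: if toxicity follow-up is then incomplete, not evaluable.
- 3.1.2, 4.6 and 6.3: replaced. 4.2, item 27: not replaced.

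**2. Which endpoints are exposed, by time of withdrawal.** Section 8.5.1 has seven research draws: days 1, 30 and 60, pre-surgical, 30 and 100 days after surgery, and 12 months. The DLT window (6.3) ends at the later of 30 days after surgery and 100 days after the last dose. On the nominal schedule of Section 3.1.4, radiation ends about day 35, surgery is 6 to 8 weeks later (day 35 + 42 = 77 to 35 + 56 = 91), and the last dose is on day 60.
- Window end: the later of day 107 to 121 (surgery + 30) and day 160 (60 + 100), so day 160.
- 30-day draw: day 107 to 121, inside the window.
- 100-day draw: day 177 to 191, after the window. The 12-month draw is later still.

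Withdrawal before surgery exposes surgery timing and later DLTs. Withdrawal around the 30-day draw exposes the rest of the DLT window but not feasibility, which is settled by then. Withdrawal at the last two draws affects mainly recurrence.

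**3. Room in the sample size.** The plan's figure of 20 equals 16/(1 − 0.20) = 20. The stated drop-out of about 10% would need 16/(1 − 0.10) = 17.8, so 18. The margin is 20 − 16 = 4 non-evaluable patients per cohort before Section 12.1 calls for an amendment.

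**4. Effect of one lost patient, not replaced** (exact binomial 95% intervals, the method of 12.3.1). With k events in 16:
- if the lost patient would have had the event, the estimate falls by k/16 − (k − 1)/15 = (16 − k)/240;
- if not, it rises by k/15 − k/16 = k/240.

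| Observed | Lost patient | Becomes | Shift |
|---|---|---|---|
| DLT 4/16 = 25% (7.3 to 52.4%) | would have had a DLT | 3/15 = 20.0% (4.3 to 48.1%) | −12/240 = −5.0 points |
| DLT 4/16 | no DLT | 4/15 = 26.7% (7.8 to 55.1%) | +4/240 = +1.7 points |
| Surgery on time 12/16 = 75% (47.6 to 92.7%) | would have been delayed | 12/15 = 80.0% (51.9 to 95.7%) | +5.0 points |
| Surgery on time 12/16 | would have been on time | 11/15 = 73.3% (44.9 to 92.2%) | −1.7 points |

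With 0 events, the upper limit moves from 20.6% (0/16) to 21.8% (0/15). Replacement restores the denominator but not the missing outcome.

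**5. Stopping rule.** Recomputing the Beta(0.05, 0.95) rule gives a boundary of 3 DLTs at 5 to 7 patients, as in Table 10.1. At the six-patient pause, 3/6 suspends accrual. If one of those three DLTs went unobserved and the patient left the evaluable set, 2/5 would not.

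**The case against.** A reader might infer more than the documents support.

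- **That 8.7 flatly contradicts 4.5.** It does not. Section 4.5 asks the question separately but never says that a patient who withdraws only samples stays on study. This is an unreconciled gap, made worse by the missing condition in 8.7.
- **That declining one blood draw removes the patient.** Section 8.6.11 describes the sampling schedule as suited to an ideal subject and lets it be modified. Nothing equates a missed draw with withdrawal of consent.
- **That the DLT rate is biased downwards because unwell patients refuse samples.** This is plausible but not shown. Nothing in the plan discards data already collected unless consent to their use is also withdrawn, or a DLT already recorded. The last two post-surgical draws fall outside the DLT window in operated patients.
- **That a definite share of primary data is lost.** No refusal rate is given, and a patient's whole record is not lost.
- **That all required samples serve only exploratory ends.** Section 8.3 requires pre-treatment tissue for diagnosis as well, and resection specimens yield pathologic response, a secondary endpoint.

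It can also be argued that the investigators may make sampling a condition of a pilot with translational aims, that Section 3.1.6.2 provides weekly record review of treated patients, and that Section 4.4 keeps patients who stop study drug in safety follow-up. The first is a legitimate choice, but it does not require giving up safety follow-up from a willing patient. The other two do not settle the matter: 4.4 excepts withdrawn consent, and 3.1.6.2 does not say that review continues after withdrawal from participation.

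**Conclusion.** The point holds in a limited form. Followed as written, 8.7 can stop in-study collection of primary-endpoint and recurrence observations from a treated patient who objects only to required sampling, and 4.5 does not prevent it. The loss covers observations after the withdrawal only; survival follow-up continues by default, and refusing leftover use alone has no such effect.

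The size is about 2 to 5 points per lost patient at the plan's 25% and 75% benchmarks, with a possible effect on a stopping boundary at small numbers. This assumes that the trigger of 8.7 is withdrawal of consent for required samples, that the 4.5 consequences apply to a patient removed under 8.7, and that the patient is not replaced. Frequency is unknown, so no total loss or direction of bias can be stated. The conflict over replacement leaves the analysis set for such patients undefined.

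**What to change.** - Restore the missing condition in 8.7, so that the trigger is explicit.
- State in both 8.7 and 4.5 that a samples-only withdrawal ends further research sampling and triggers sample disposal, while DLT and adverse-event, surgery-timing, recurrence and survival follow-up continue in the study if the patient agrees.
- State that such patients stay in the primary safety and feasibility analyses.
- Reconcile Section 4.2, item 27, with Sections 3.1.2, 4.6 and 6.3 on replacement.
- Reconcile 8.7 and 4.5 on whether study treatment continues after a samples-only withdrawal. No rule on that is proposed here.

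The cost is a few sentences and matching consent wording. The downside is incomplete exploratory samples for those patients, and these would be lost in any case.
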